To prepare an infusion solution concerning 4 mg Zoledronic acid Actavis further dilute the Zoledronic acid Actavis concentrate (5,0 ml) with 100 ml calcium-free or other divalent cation-free infusion solution. If a lower dose of Zoledronic acid Actavis is required, first withdraw the appropriate volume as indicated below and then dilute it further with 100 ml of infusion solution. To avoid potential incompatibilities, the infusion solution used for dilution must be either 0.9% w/v sodium chloride or 5% w/v glucose solution.

Introduction for preparing reduced dose of Zoledronic acid Actavis:

Withdraw the appropriate volume of the liquid concentrate, as follows:

- » 4.4 ml for 3.5 mg dose
- » 4.1 ml for 3.3 mg dose
- » 3.8 ml for 3.0 mg dose

The solution containing zoledronic acid is given as a single 15-minute intravenous infusion in a separate infusion line. The hydration status of patients must be assessed prior to and following administration of Zoledronic acid Actavis to ensure that they are adequately hydrated.

Do not mix Zoledronic acid Actavis concentrate with calcium-containing or other divalent cation containing solution such as lactated Ringer's solution. Since no data are available on the compatibility of Zoledronic acid Actavis with other intravenously administered substances. Zoledronic acid Actavis must not be mixed with other medications/substances and should always be given through a separate infusion line.

For single use only. Any unused solution should be discarded. Only clear solution free from particles and discolouration should be used. Aseptic techniques must be followed during the preparation of the infusion.

Healthcare professionals are advised not to dispose of unused Zoledronic acid Actavis via the domestic sewage system. Any unused medicinal product or waste material should be disposed of in accordance with local requirements.

The recommended dose in the prevention of skeletal related events in patients with advanced malignancies involving bone is 4 mg zoledronic acid every 3 to 4 weeks. Patients should also be administered on oral calcium supplement of 500 mg and 400 IU vitamin D daily. The decision to treat patients with bone metastases for the prevention of skeletal related events should consider that the onset of treatment effect is 2-3 months.

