9.1.2 Classification by severity

The related adverse events will be classified as mild, moderate or severe according to the following criteria:

- Mild: symptoms do not alter the normal functioning of the Patient
- Moderate: symptoms cause some degree of dysfunction of the Patient, but are not dangerous, unpleasant or embarrassing to the Patient.
- Severe: symptoms are clearly dangerous for the Patient, cause significant impairment functioning or disability.

9.1.3. Classification according to the a causal relationship between the use of the administered drug and the occurrence of an adverse event

In the Study only adverse events data showing a causal-and-effect relationship with the administration of the study medicinal product will be collected.

Submission of possible and probable (likely time sequence, dose-response relationship) and certain adverse events (good response to discontinuation of the drug or the severity of the adverse events after restarting the drug) related to study medicinal product use will be reported. This report should also include the correct reason and comprehensive information covering the likely time sequence, a good response to treatment withdrawal/reduction of the dose or the severity of the adverse event after restarting the drug/increase the dose; another used pharmacotherapy and procedures – dose decrease, drug withdrawal, optional treatment administered, the effect of used procedure.

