10.4.3. The safety assessment

All safety data will be included in the summaries of data on individual patients. Analysis and summary tables are based on data from the safety population

The related adverse events will be coded in accordance with Medical Dictionary for Regulatory Activities (Med-DRA).

The prevalence of all reported related adverse events and serious adverse events occurring during the study drug administration will be presented in the form of tables. In addition, summary tables will be presented, that will include data on the maximum severity, relationship to the study drug administration and related data on adverse events, and patients who discontinued treatment with study drug for any reason.

The related adverse events occurring during the study will be noted in the tables related to adverse events. Medication usage due to concomitant disease will be summarized with the number and percentage of patients receiving them divided into a group of pharmacological and generic name of the drug.

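### As printed, 'moderate' leaves unpleasant, partly limiting events without a severity grade; 'certain' can rest on dechallenge alone, and 'possible' and 'probable' share one criterion

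*Protocol*

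**What the plan says.** **Severity (Protocol, Section 9.1.2).** There are three grades. The middle one reads "Moderate: symptoms cause some degree of dysfunction of the Patient, but are not dangerous, unpleasant or embarrassing to the Patient". Below it, an event is mild if the patient functions as before; whether it is unpleasant plays no part. Above it, the top grade reads "Severe: symptoms are clearly dangerous for the Patient, cause significant impairment functioning or disability".

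**Causality (Protocol, Section 9.1.3).** Entry is restricted: "In the Study only adverse events data showing a causal-and-effect relationship with the administration of the study medicinal product will be collected". Within the events admitted, two categories are described together as "possible and probable (likely time sequence, dose-response relationship", closed by a single bracket. The third is given as "certain adverse events (good response to discontinuation of the drug or the severity of the adverse events after restarting the drug". The same section asks the report to cover timing, the course after withdrawal or restart, and other drugs and procedures.

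**Use (Protocol, Section 10.4.3).** Summary tables are planned "that will include data on the maximum severity, relationship to the study drug administration".

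**Dosing background (Protocol, Section 1.2).** For prevention of skeletal events the recommended dose "is 4 mg zoledronic acid every 3 to 4 weeks", given as a 15-minute infusion.

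**The concern.** A severity scale should give every event exactly one grade, and a causality scale should have categories that a rater can tell apart. Neither holds here.

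The severity gap falls where a middle grade is most needed. The list of common reactions in Section 1.2 includes headache, nausea, vomiting, bone pain, myalgia, arthralgia, fever and flu-like syndrome. Such reactions are usually unpleasant (my judgement, not a statement in the protocol). When one of them partly limits the patient, the physician must grade it down, grade it up or disregard the text, and physicians may choose differently.

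On causality, the top category can be reached by dechallenge alone. With an intermittent infusion, a transient reaction may clear before the next dose would have been due whether or not treatment is stopped, so improvement after stopping says little about cause. Because only events already judged related are collected, the relationship category is the only causal gradation in the data.

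Safety is the main aim (Section 2.1). Investigators assign these grades under the protocol's definitions, so a later statistical analysis plan could not restore distinctions that were never recorded.

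**Working it through.** No figure in the plan is at issue: the study is descriptive, and Section 10.3 says its size of about 3,500 has no statistical basis. The check is one of logic.

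**Step 1. Severity, all combinations.** Inputs are the three definitions in Section 9.1.2. I crossed functioning (unaffected, some dysfunction, significant impairment or disability) with dangerous (no, yes) and unpleasant or embarrassing (no, yes): 3 × 2 × 2 = 12 situations. 'Dangerous' and 'clearly dangerous' are treated as the same thing. The text does not settle whether the severe criteria are alternatives or joint conditions, so both readings are shown.

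| Functioning | Dangerous | Unpleasant | 'Severe' if any criterion | 'Severe' if all criteria |
|---|---|---|---|---|
| unaffected | no | no | mild | mild |
| unaffected | no | yes | mild | mild |
| some dysfunction | no | no | moderate | moderate |
| some dysfunction | no | yes | **none** | **none** |
| significant | no | no | severe | **none** |
| significant | no | yes | severe | **none** |
| unaffected | yes | either | mild and severe | mild |
| some dysfunction | yes | either | severe | **none** |
| significant | yes | either | severe | severe |

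Each row marked 'either' stands for two situations.

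- Any-of reading: 1 of 12 has no grade, 2 of 12 have two grades, and 9 have exactly one.
- All-of reading: 5 of 12 have no grade, and 7 have exactly one.
- Among the three non-dangerous unpleasant situations, 1 of 3 is ungraded under any-of and 2 of 3 under all-of.
- The cell with some dysfunction, not dangerous and unpleasant is empty under both readings.

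**Step 2. Would the likely intended sense help?** If 'moderate' meant not dangerous but possibly unpleasant or embarrassing, that cell becomes moderate under both readings. The printed sentence does not say so: its negation governs all three adjectives. The mild/severe overlap under any-of, and the other empty cells under all-of, would remain.

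**Step 3. Causality, category by category (Section 9.1.3).**

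| Category | Criterion printed | Alternative cause a criterion? |
|---|---|---|
| possible | timing, dose-response | no |
| probable | the same bracket as possible | no |
| certain | good response to stopping, *or* course after restart | no |

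The first two rows are identical, so nothing separates them. In the third, the 'or' makes either limb sufficient, so 'certain' needs neither rechallenge nor exclusion of another cause.

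**Step 4. How informative is dechallenge here?** Section 1.2 gives infusions 3 to 4 weeks apart and plasma levels below 1% of peak after 24 hours. Section 9.2 calls for stopping the drug when an event is still present the day after it was recorded. If that is followed, an event that outlasts a day and then clears by itself comes after a discontinuation and could be recorded as a good response.

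**Step 5. Can the number of events be sized?** No. Section 1.2 puts common reactions at 1/100 to below 1/10. For one such term in 3,500 patients, that is 3,500 × 0.01 = 35 to just under 3,500 × 0.1 = 350 patients. These are patients with the reaction, not patients in the empty cell. The protocol does not give the share with partial dysfunction, or the share that would be called 'certain' on dechallenge alone.

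**Step 6. The proposed severity wording (see the fix), through the same 12 situations.** Two are mild (unaffected, not dangerous), two moderate (some dysfunction, not dangerous) and eight severe. None is ungraded and none has two grades.

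**The case against.** **It is probably a translation slip.** The English is rough elsewhere, and the intended sense may well have been not dangerous but unpleasant. That is plausible, but the printed sentence is the rule raters would apply. It argues for a cheap correction, not for leaving the text.

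**Alternative causes are recorded.** Section 9.1.3 asks for other therapy and procedures, Section 6.2 for the course and treatment of the primary disease, Section 8.3 for concomitant drugs at every visit, and Section 9.2 for an investigator's causality assessment. This stands as far as it goes: the information exists, but it does not decide the category.

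**The reach is limited.** Event frequencies, MedDRA coding, seriousness and expectedness do not use these scales. No comparison between centres is described in Section 10.4, and Section 10.3 disclaims definitive safety conclusions. All of this stands.

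A reader might infer three stronger things that the protocol does not support:

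- *That every unpleasant, non-dangerous event lacks a grade.* Mild depends only on functioning, and significant impairment is severe under the any-of reading. The gap common to both readings is at some dysfunction.
- *That any event resolving off drug is 'certain'.* The category applies only to events already judged related, and it requires a response to an actual discontinuation. Clearing between scheduled infusions is not, by itself, discontinuation.
- *That both tables must misclassify events or cannot be interpreted.* The definitions create that risk. Nothing in the protocol shows how often it would occur.

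**Conclusion.** The point holds in a limited form. The severity grades are not exhaustive: a non-dangerous, unpleasant event with some dysfunction has none, whichever way 'severe' is read. The any-of reading also lets a dangerous event that leaves functioning intact be both mild and severe. The causality categories are not distinct: 'possible' and 'probable' coincide, 'certain' may rest on dechallenge alone, and other causes play no defining part.

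Two tables are affected, maximum severity and relationship to study drug; counts of related events are not. The size is 1 of 3 non-dangerous unpleasant situations ungraded (2 of 3 under the all-of reading), with no number of events computable. The conclusion rests on reading the printed English literally and on treating the two phrases for danger as one. The weakness of dechallenge is argued for transient reactions only. The wording should be corrected, because the rules are applied when the data are recorded.

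**What to change.** **Section 9.1.2.** Reword moderate as: some dysfunction; may be unpleasant or embarrassing, but is not dangerous. State that severe applies if any one of clear danger, significant impairment or disability is present, and that it takes precedence over the lower grades. Use the same term for danger in both grades.

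**Section 9.1.3.** Give each category its own criteria:

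- *Possible*: plausible timing, with another cause also plausible.
- *Probable*: plausible timing, with another cause unlikely.
- *Certain*: plausible timing, no other plausible cause, a good response to discontinuation, and recurrence if the drug was in fact given again in routine care. Events without re-exposure are graded no higher than probable.

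These are labels for events as they occurred. They do not call for re-exposure, discontinuation or any other change in treatment.

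**Cost.** New wording in the two sections and on the Observation Form, with no new data items beyond what the report already asks for. The downside is that fewer events will be labelled 'certain'.

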9.1.4. Assessment of expectedness

Whether a particular adverse event can be defined as an expected adverse reaction should be determined in accordance with the information contained in the approved Summary of Product Characteristics (SPC) or the Patient leaflet accompanying the authorization of the drug. Reference document for evaluating whether a particular adverse reaction can be defined as expected is in this study the current approved Summary of Product Characteristics, Polish version.

9.1.5. Deviations in the results of laboratory tests

Liver enzymes, total blood count, serum creatinine, uric acid and electrolytes concentrations, if these tests were made.

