In multiple myeloma patients, the risk of renal dysfunction may be increased when Zoledronic acid Actavis is used in combination with thalidomide.

Caution is advised when Zoledronic acid Actavis is administered with anti-angiogenic medicinal products, as an increase in the incidence of osteonecrosis of the jaw (ONJ) has been observed in patients treated concomitantly with these medicinal products.

The adverse events related to use of **ZOLEDRONIC ACID ACTAVIS** formulation, including: (Summary of Product Characteristics, Zoledronic acid Actavis 4 mg/5 ml concentrate for solution for infusion, dated 08-01-2015, EMEA/H/C/002488)

Very common (≥1/10): hypophosphataemia

Common (≥1/100 to <1/10): anaemia, headache, conjunctivitis, nausea, vomiting, decreased appetite, bone pain, myalgia, arthralgia, generalised pain, renal impairment, fever, flu-like syndrome (including fatigue, rigors, malaise and flushing), blood creatinine and blood urea increased, hypocalcaemia

Uncommon (≥1/1000 to <1/100): thrombocytopenia, leukopenia, hypersensitivity reaction, anxiety, sleep disturbance, dizziness, paraesthesia, dysgeusia, hypoaesthesia, hyperaesthesia, tremor, somnolence, blurred vision, scleritis, orbital inflammation, hypertension, hypotension, arterial fibrillation, hypotension leading to syncope and circulatory collapse, dyspnoea, cough, bronchoconstriction, diarrhoea, constipation, abdominal pain, dyspepsia, stomatitis, dry mouth, pruritus, rash (including erythematous and macular rash), increased sweating, muscle spasms, osteonecrosis of the jaw, acute renal failure, haematuria, proteinuria, asthenia, peripheral oedema, injections site reactions (including pain, irritation, swelling, induration), chest pain, weight increase, anaphylactic reaction/shock, urticaria, hypomagnesaemia, hypokalaemia

Rare (≥ 10 000 to <1/1 000): pancytopenia, angioneurotic oedema, confusion, uveitis, bradycardia, cardiac arrhythmia (secondary to hypocalcaemia), interstitial lung disease, arthritis and joint swelling as a symptom of acute phase reaction, hyperkalaemia, hypernatraemia, atypical subtrochanteric and diaphyseal femoral fractures

Very rare (< 10 000): Convulsions, hypoaesthesia and tetany (secondary to hypocalcaemia) episcleritis

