3.3. Substantiation of the study construction

Non-interventional, post-marketing study assessing the safety of treatment with **ZOLEDRONIC ACID ACTAVIS**. In study patients no additional diagnostic procedures or monitoring and analysis will be performed and in analysis of the collected data, epidemiological methods only, will be used.

The aim of the study is to collect data on any adverse events that may occur during the routine use of ZOLEDRO-NIC ACID ACTAVIS in the Polish population, according to the indications and other information contained in the Summary of Product Characteristics.

The study will be conducted in approximately 3,500 patients who were treated with a ZOLEDRONIC ACID ACTAVIS formulation as part of routine therapy. Observation of the safety using the study drug by one patient will last for four months due to the chronic nature of the therapy. During this time, centers will gather data on any adverse events of ZOLEDRONIC ACID ACTAVIS that will be recorded in Observation Form and reported to the company Europharma M. Rachtan Sp. z o.o. Please see section 9.

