10.2. Analysis, population, definition

Safety population: All patients who received at least one dose of study drug.

The safety data analysis will be conducted on the safety population.

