10.3. The method of determining the sample size

This is a non-interventional study in which the number of patients about 3,500 was determined taking into account the practical limitations, and not on the basis of statistical analysis. Therefore, this study does not make up the basis for the formulation of definitive conclusions about the safety of the study drug.

This is a descriptive study evaluating safety and tolerance of treatment with study drug, thus in this study basic statistical analysis will be performed.

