10.4. Statistical methods

On the basis of reported adverse events, the frequency of their occurrence in study population will be assessed. For the most common adverse events the characteristics of subpopulation in which it was reported will be analyzed.

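### Laboratory-detected reactions are recorded only in patients who were tested but counted over all treated patients, with no record of who was tested, so their frequencies are understated by an unknown amount

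*Protocol*

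**What the plan says.** Section 9.1.5 of the protocol defines the laboratory deviations to be captured as "Liver enzymes, total blood count, serum creatinine, uric acid and electrolytes concentrations, if these tests were made". Section 3.3 rules out study-mandated testing: "In study patients no additional diagnostic procedures or monitoring and analysis will be performed". Section 11 repeats this.

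Section 10.2 sets the population: "Safety population: All patients who received at least one dose of study drug". It adds: "The safety data analysis will be conducted on the safety population". Section 10.4 says of the reported events that "the frequency of their occurrence in study population will be assessed", and section 10.4.3 says "Analysis and summary tables are based on data from the safety population".

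The schedule in section 6.1 has no laboratory line. The data lists for Visits 1 and 2 in section 6.2 do not record whether a patient was tested. Section 7.1.2 collects events through questions asked at the visit.

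The product information reproduced in section 1.2 gives the expected frequencies. Its top band reads "Very common (≥1/10): hypophosphataemia". Hypocalcaemia and raised creatinine are listed as common, and hypomagnesaemia as uncommon. The same section calls for creatinine before each dose, and for monitoring of calcium, phosphate and magnesium after the start of therapy, with no interval stated.

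**The concern.** A fall in phosphate, calcium or magnesium is found mainly by a blood test. If no test was done, asking the patient will usually not reveal it. Followed as written, the plan puts such a patient in the denominator with no chance of contributing an event, so not measured is displayed in the same way as not occurring.

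Safety is the main aim of the study, and the event frequency is its main output. For these reactions the displayed percentage depends partly on how often centres test. Without the number tested, a reader who sees a low percentage cannot tell few reactions from few tests. A later analysis plan could change the denominator, but it could not identify tested patients with normal results if test status had never been collected.

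**Working it through.** **Plan's own figure.** There is none to reproduce. The sample of about 3,500 "was determined taking into account the practical limitations, and not on the basis of statistical analysis" (section 10.3), and the protocol gives no expected rate and no share tested.

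**Inputs**
- p: the true risk, among all treated patients, of a laboratory event that would be recorded if tested. I take p = 10%, the lower limit of the very common band in section 1.2.
- t: the share of patients tested for the analyte. Assumed, 50% to 90%.
- r: the risk in untested patients divided by the risk in tested patients. Assumed, 0 to 1.
- n = 3,500 from section 10.3.

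**Formulas**
- Overall risk is the weighted sum over tested and untested patients, so risk in the tested = p / (t + (1 − t)r). This is also what a tested-only denominator displays.
- Display over all patients = p·t / (t + (1 − t)r).
- Relative loss over all patients = 1 − t / (t + (1 − t)r).

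With r = 1 the bracket equals 1, and the loss is 1 − t, the share untested. With r = 0 the loss is zero.

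**Results for p = 10%**

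| Share tested | r | Display, all patients | Relative loss | Display, tested only |
|---|---|---|---|---|
| 90% | 1 | 9.0% | 10% | 10.0% |
| 70% | 1 | 7.0% | 30% | 10.0% |
| 50% | 1 | 5.0% | 50% | 10.0% |
| 90% | 0.5 | 9.5% | 5.3% | 10.5% |
| 70% | 0.5 | 8.2% | 17.6% | 11.8% |
| 50% | 0.5 | 6.7% | 33.3% | 13.3% |
| 90% | 0 | 10.0% | 0% | 11.1% |
| 70% | 0 | 10.0% | 0% | 14.3% |
| 50% | 0 | 10.0% | 0% | 20.0% |

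One row written out, for t = 0.7 and r = 0.5: the bracket is 0.7 + 0.3 × 0.5 = 0.85. The all-patient display is 10% × 0.7 / 0.85 = 8.2%, the loss is 1 − 0.7 / 0.85 = 17.6%, and the tested-only display is 10% / 0.85 = 11.8%. The relative losses do not depend on p.

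**Bracketing.** The all-patient figure cannot exceed p. The tested-only figure is at least p whenever r is 1 or less. The two figures therefore bracket p for r between 0 and 1, but not if untested patients are at higher risk.

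**Precision.** The 95% half-width is 1.96 × √(p(1 − p)/n). At p = 10% it is 1.96 × √(0.09/3,500) = ±1.0 points. With half the patients tested it is 1.96 × √(0.09/1,750) = ±1.4 points.

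**The case against.** **Testing may be close to complete.** Sections 3.1 and 6.2.1 say that treatment follows the product information, and section 1.2 calls for creatinine before each dose and careful monitoring of calcium, phosphate and magnesium. This stands for creatinine and may stand for the others, although no interval is stated for them. It limits the likely size of the problem, but the plan as written could not show that testing was complete.

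**Row denominators belong in an analysis plan, and the Observation Form is not shown.** This stands in part. Naming the safety population does not forbid a per-analyte count within it, and the form may already have a box for each test. But the protocol lists what is recorded at each visit, and test status is not there. That is a matter of data capture which no later plan can repair.

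**The study is descriptive.** Section 10.3 disclaims definitive conclusions about safety. That lowers the stakes, but a descriptive percentage still needs an interpretable denominator.

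**Stronger readings that the documents do not support.**
- A reader might infer that the frequencies are understated by exactly the share untested. That needs equal risk in tested and untested patients. Section 1.2 describes hypocalcaemia severe enough for hospital admission, so some testing may well be prompted by symptoms, and the loss would then be smaller.
- A reader might also infer that hypophosphataemia will drop out of the very common band. That depends on the inputs chosen. With equal risk, a true 12% falls below 10% if fewer than 10/12 = 83% are tested, whereas a true 15% with 80% tested shows 12% and stays above. The protocol plans no reclassification by band.
- Recording results only where a test was done is not itself an error in a non-interventional study.

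**Conclusion.** The point holds as a weakness of denominator and data capture. Frequencies of reactions found mainly by blood test will be too low whenever some patients are untested and those patients carry some risk. The size is unknown, because the protocol gives neither the share tested nor any way to learn it. With equal risk, the relative loss is 10%, 30% or 50% at 90%, 70% or 50% tested. With half the risk in untested patients it is 5.3%, 17.6% or 33.3%. The share untested is an upper limit on the loss only if untested patients are at no higher risk than tested ones. All shares tested and risk ratios here are assumptions, and the true share tested may be high, so the actual effect may be small.

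A separate limit applies whatever the denominator. Section 9.1.3 collects only events judged related to the drug, which lowers laboratory frequencies even with complete testing. The figures above concern recorded, drug-related events, not all laboratory abnormalities. This is a cheap improvement worth making, not a flaw that invalidates the study.

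**What to change.** 1. In sections 6.1 and 6.2 and in the Observation Form, add a yes/no entry for each analyte stating whether it was tested: at Visit 1 since the start of the drug, and at Visit 2 since Visit 1. The Visit 1 window must reach back to the start of treatment because section 7.1.2 also collects events from before enrolment.
2. In section 10.4.3, report each laboratory-detected event twice: over all safety patients, and over patients with at least one on-treatment result for that analyte. Print the number tested beside it.
3. State in the report that the two figures bracket the risk of recorded, drug-related laboratory events only if untested patients are at no higher risk than tested ones, and that the related-only rule in section 9.1.3 lowers both.

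The cost is a few tick boxes per visit and one extra column in the tables. The tested-only figure is less precise (at 10%, about ±1.4 points with 1,750 tested against ±1.0 with 3,500) and may overstate risk if testing is prompted by symptoms, which is why both figures should be shown. No extra tests are needed, so the study stays non-interventional.
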